## SUMMARY OF FINAL PROTOCOL & AMENDMENTS

| Initial/
Amend # | Version Date         | Author     | Main Changes |
|---------------------|----------------------|------------|--------------|
| Final        | 21 March 2018 | [REDACTED] | N/A          |
| A1           |                      |            |              |
| A2           |                      |            |              |
| A3           |                      |            |              |

# 1. PROTOCOL SYNOPSIS

**Table 1: Protocol synopsis**

|  |   |   |
|--|---|---|
| Protocol Title                        | The Effect of Manuka Eye Drops on Tear Film Properties  |   |
| Protocol ID Number                    | SOVS2018-501  |   |
| Trial Classification                  | Evaluation  |   |
| Investigator(s)/Site(s)               | Eye Research Group @ SOVS
The University of New South Wales
Sydney, Australia   |   |
| Overall Duration of Trial             | 4 months  |   |
| Number of Trial Participants Planned  | 48  |   |
| Planned Start Date                    | June 2018   |   |
| Primary Objective                     | To compare the effect on tear film properties and dry eye signs and symptoms of Optimel Manuka eye drops compared to Systane Ultra tear supplement after one month of daily use.  |   |
| Secondary Objectives                  | 
 
To compare the effect on ocular signs and symptoms.
 
   |   |
| Primary Safety Variable(s)            | Visual acuity
Biomicroscopy: ocular redness, corneal details and staining  |   |
| Primary Efficacy/Performance Variable | Lipid layer thickness, tear evaporation rate and fluorescein tear breakup time up   |   |
| Experimental design                   |  Retrospective
 Prospective
 Single group
 Multiple group
 Parallel group
 Cross over
 Contralateral  |  Single masked (Trial Participant)
 Single masked (Investigator)
 Double masked
 Sponsor masked
 Open label
 Other: randomised |
| Study product details - test          | Name   | Optimel™ Manuka+™ Dry Eye Drops   |
|  | Manufacturer   | Melcare Biomedical Pty Ltd  |
| Study product details - control       | Name   | Systane Ultra   |
|  | Manufacturer   | Alcon Laboratories  |
| Inclusion criteria                    | 
 
○ Able to read and comprehend English and give informed consent as demonstrated by signing a record of informed consent;
 
○ General population aged 18 years and over;
 
○ In good general health;
 
○ Subjectively experiencing dry eye symptoms (e.g. burning, irritation, and discomfort due to dryness of the eye or exposure to wind or sun). Participants will be selected based on a minimum OSDI score of 13 points (1).
 
○ Willing to discontinue CL wear for 1 week before first visit and continue to do so until the conclusion of the study;
 
○ Participant is willing to discontinue their use of any previous conventional dry eye treatment method commenced before the study throughout the study;
 
○ Willing to comply with the dosage and study visit schedule as directed by the investigator;
 
○ No planned changes to diet and willing not to substantially alter
 
 |   |

|   |   |
|---|---|
|   | 
their usual diet for the duration of the study, including their typical intake of fish, green tea or oral supplements known to have anti-inflammatory properties;
 
 
○ Willingness to notify the study investigator if instructed to alter their diet by health/medical practitioner.
 
   |
| Exclusion criteria   | 
 
○ Allergy to benzoic acid preservatives;
 
○ Allergy to honey products;
 
○ Active anterior eye disease/ infection, inflammation/allergy that requires ocular medical treatment;
 
○ Eye injury or surgery in the past 6 months including chemical burns, penetrating injuries, traumatic iritis, orbital fractures, laser surgery, strabismus surgery, cataract or any other intraocular surgeries;
 
○ Soft contact lens, rigid gas permeable, orthokeratology lens wearer within one week prior to the study and during the study.
 
○ Use of any of the following medications (including steroids) up to 12 weeks prior to start of the study or during the course of the study:             
 
- Ocular medication, category S3 and above;
 
- Any systemic or topical medications that will affect ocular physiology e.g. anti-acne medications such as Roaccutane and corticosteroid or immunosuppressant medications such as Hydrocortisone, Prednisolone and antihistamine medications such as Claritine;
 
 
 
○ Any systemic disease that may affect ocular health e.g. Graves disease, and auto-immune diseases such as ankylosing spondylitis, multiple sclerosis and systemic lupus erythematosus;
 
○ Epilepsy or history of migraines exacerbated by flashing, strobe-like lights;
 
○ The Investigator may, at his/her discretion, exclude anyone else who they believe may not be able to fulfil the study requirements, or if it is believed to be in the participant's best interests.
 
 |
| Human Research Ethics Committee Status / Regulatory Status | 
This trial requires Human Research Ethics Committee approval prior to study initiation, any advertising, and participant consent/enrolment.
 
The study products are commercially available in Australia and are approved by the Therapeutic Goods Administration.
  |

## 4. BACKGROUND INFORMATION

### 4.1 Product

Optimel Manuka eye drops (MelCare Biomedical Pty Ltd., Australia) is at present the only available manuka based eye drop commercially available in Australia. It is available both as 16% eye drop as well as 98% gel form^1. Presently, a growing number of studies are exploring ocular benefits of the drop, based on extensive evidence of antimicrobial, antioxidant, and anti-inflammatory effects of Manuka honey.

Systane Ultra lubricant eye drops (Alcon Laboratories, Inc., Forth Worth, Tx) is a new generation ocular lubricant that has been developed with a unique intelligent delivery system for the treatment of dry eye symptoms. It is an aqueous solution composed of polyethylene glycol (0.4%) and propylene glycol (0.3%) as demulcents and incorporates the benefits of hydroxypropyl guar as gelling agent.

### 4.2 Summary

This study is potentially significant in its demonstration of the benefits of Manuka honey eye drops in altering the physiological properties of the tear film, thereby improving ocular comfort and reducing dry eye. These findings will aid in informing practitioners about the benefits of considering Manuka eye drops in the alleviation and treatment of dry eye disease, whilst adding credibility to the Optimel Manuka eye drops range and growing its potential market opportunities globally.

#### 4.2.1. Risks and Benefits

##### Risks of the Clinical Trial

Although unlikely, it is possible that participants may be allergic to any of the ingredients in the study eye drops. Signs of ocular allergy include swelling, redness, itching and watering of the eyes. Subjects with a known allergy to the study eye drops will not be enrolled. Subjects who experience an allergic reaction will be treated by thoroughly rinsing the eye with preservative free unit-dose saline, continuous monitoring until ocular signs and symptoms have returned to normal, and immediate discontinuation from the study. Subjects may also be referred to the Sydney Eye Hospital for treatment, if required.

##### Benefits of the Clinical Trial

There is no guarantee or promise that the participants will receive any benefits from this clinical trial.

#### 4.2.2. Treatment Rationale

This is a prospective, randomized, double-masked, single centre study. All eligible participants were randomized into one of the treatment groups. One group received Optimel Manuka eye drops (Leptospermum spp. honey 160 mg/g, water, sodium chloride, benzoic acid 0.2 per cent) (Optimel 16 percent), (Melcare, Australia) and the other group received a non-lipid based conventional ocular lubricant, Systane Ultra (Polyethylene Glycol 400 0.4%, Propylene Glycol 0.3%, aminomethylpropanol, boric acid, hydroxypropyl guar, POLYQUAD® (polyquaternium-1) 0.001% preservative, potassium chloride, purified water, sodium chloride, sorbitol)(Alcon

Laboratories, USA). Participants were asked to instill one drop into each eye, three times a day for twenty-eight days ( $\pm 4$  days).

#### **4.2.3. Guidelines and Regulations**

The clinical trial will be conducted in accordance with the protocol, the Declaration of Helsinki (see Appendix 1), ICH GCP and local regulations as applicable including TGA and NH&MRC guidelines.

#### **4.2.4. Trial Population**

Thirty-eight (38) participants aged 18 years or above who were assessed to have mild to severe dry eye are required to complete the study. Taking into consideration a 20% drop out rate, approximately 48 subjects will be enrolled in this study.

## 5. TRIAL OBJECTIVES AND CLINICAL HYPOTHESIS

### 5.1. *Trial Objective*

To compare the effects of Optimel Manuka eye drops and Systane Ultra on symptomology assessed using the OSDI questionnaire, and objective tear film properties such as lipid layer thickness and tear break-up time will be measured 4 weeks after use of treatment drops in dry eye participants.

### 5.2. *Clinical Hypothesis*

We hypothesize that the:

- Measurable differences in the subjective symptomatology and in objective tear film parameters will be apparent after 4 weeks of use with the Optimel Manuka and Systane Ultra eye drop treatments.

## 6. TRIAL DESIGN

This will be a prospective, randomized, single centre, double-masked, randomized dispensing study. There will be 2 visits in total:

- (i) **Baseline (Week 0):** Screening, randomization, informed consent, habitual visual acuity, OSDI, symptom survey, biomicroscopy, tear film assessment and dispensing eye drops.
- (ii) **28 days of treatment  $\pm$  4 days (Week 4):** habitual visual acuity, OSDI, symptom survey, biomicroscopy, tear film assessment and study exit.

Standard ocular examination and non-standard ocular examination procedures will be carried out at the scheduled visits.

*Standard optometric procedures at each visit include:*

- Habitual visual acuity
- Slit lamp evaluation including corneal details
- Subjective questionnaire: Ocular Surface Disease Index (OSDI)
- Tear breakup time
- Tear lipid layer thickness

*Non-standard optometric procedures may include:*

- Tear evaporation rate

### 6.1. Methodology / Study Visits

#### 6.1.1. Data Requirements per Visit

This study requires 2 visits of approx. 1-hour duration each. The data requirements for each visit are shown in Table 4.

**Table 4: Data requirements**

| Procedures/ Data (Y/N)                         | Visit 1
Screening / Baseline | Visit 2
28 days ± 4 days |
|---|---|-------------------------------------|
| Informed Consent                                      | Y                                       | N                                   |
| Meet Inclusion/Exclusion Criteria                     | Y                                       | N                                   |
| Ocular and Medical History, Medications, Demographics | Y                                       | Y                                   |
| Vision Tests (Visual Acuity)                          | Y                                       | Y                                   |
| Randomization (to eye drop)                           | Y                                       | N                                   |
| Slit-Lamp Biomicroscopy                               | Y                                       | Y                                   |
| Subjective questionnaire                              | Y                                       | Y                                   |
| Tear evaporation rate                                 | Y                                       | Y                                   |
| Tear break-up time                                    | Y                                       | Y                                   |
| Tear lipid layer thickness                            | Y                                       | Y                                   |

### 6.1.2. Randomisation and Masking

Prior to initiation of study treatment, each subject who provides informed consent will be assigned to a subject number that will serve as the subject identification number on all study documents. Subject numbers will be assigned in ascending order and should not be omitted or reused.

Participants will be randomly assigned to the eye drop type to be dispensed (Optimel Manuka+16% eye drops or Systane Ultra eye drops). A randomization scheme will be prepared in advance.

The Investigator will provide instructions to the study participants as to the drop instillation technique but will not be cognizant to the randomisation schedule and will not be present during the drop dispensation to maintain masking.

### 6.1.3. Clinical Trial Population

A total of 46 participants with dry eye disease will be required to complete the study.

Trial participants will be recruited from the local population at the investigational site. An e-mail invitation will be circulated to [REDACTED]

[REDACTED]

[REDACTED]. Advertisements may also be posted in [REDACTED]

[REDACTED]

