### 6.1.5. Enrolment

A study participant is considered enrolled when they have signed the Participant Information Statement and Consent Form.

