## SELECTION AND WITHDRAWAL OF PARTICIPANTS

### 7.1. Participant Selection

Participants with dry eye disease will be enrolled. Informed consent will be obtained prior to any clinical trial procedures being conducted. All participants will conform to the clinical trial entry criteria listed below:

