#### 7.1.1. Inclusion Criteria

- Able to read and comprehend English and give informed consent as demonstrated by signing a record of informed consent;
- Adults aged 18 years and over with symptoms of dry eye;
- Ocular Surface Disease Index score of >12 at Screening;
- Not wearing contact lenses for 1 week prior to the study and for the duration of the study;
- Willing to use the study eye drops and refrain from using any other eye drops for the duration of the study;
- Willing to refrain from using the study eye drops within 4 hours prior to each study visit;
- Willing to comply with the study visit schedule and adhere to instructions as directed by the Investigator.

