#### 13.1.1. Number of Participants

38 participants will be required to complete the study.

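### Section 6.1.3 requires 46 completers but Sections 4.2.4 and 13.1.1 require 38, and only 38 fits 48 enrolled with 20% drop-out

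*Combined protocol and SAP*

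**What the plan says.** The number of completers appears in three places:

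- Section 4.2.4: "Thirty-eight (38) participants aged 18 years or above who were assessed to have mild to severe dry eye are required to complete the study".
- Section 13.1.1: "38 participants will be required to complete the study".
- Section 6.1.3: "A total of 46 participants with dry eye disease will be required to complete the study".

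The enrolment figure appears in two. Section 4.2.4 continues: "Taking into consideration a 20% drop out rate, approximately 48 subjects will be enrolled in this study". The synopsis (Table 1) gives 48 against "Number of Trial Participants Planned".

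Section 13.1.3 restricts the analysis dataset to participants who complete study treatment.

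On what counts as enrolment, Section 6.1.5 says: "A study participant is considered enrolled when they have signed the Participant Information Statement and Consent Form". Section 7.1 adds: "Informed consent will be obtained prior to any clinical trial procedures being conducted". Table 4 places consent, the check of entry criteria and randomisation all at Visit 1, and one inclusion criterion in Section 7.1.1 is "Ocular Surface Disease Index score of >12 at Screening".

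**The concern.** All three completer statements describe people who must finish the study, so 46 and 38 cannot be read as an enrolled count and a completed count. The table of amendments lists none, so neither figure is superseded text, and the redactions in Section 6.1.3 affect the recruitment wording, not the number.

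With a completers-only analysis, the completer count is the sample size of the primary comparison. The protocol gives no effect size, SD or power from which a reader could work out which number governs. As written, nobody could say whether a trial that finished with, for example, 40 completers had met its target.

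A second, smaller question is what the 48 counts. By the definition in Section 6.1.5, a person who signs consent and then fails screening has already been enrolled.

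**Working it through.** **Inputs.** Required completers 38 (Sections 4.2.4 and 13.1.1) or 46 (Section 6.1.3); drop-out 20% (Section 4.2.4); enrolled 48 (Section 4.2.4, synopsis).

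**1. Reproduce the plan's figure.** Enrolled = completers / (1 − drop-out). With 38: 38/0.80 = 47.5, rounded up to 48. This is the stated enrolment. The 38 itself cannot be reproduced, because no effect size, SD or power is stated.

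**2. Repeat with 46.** 46/0.80 = 57.5, rounded up to 58, which is 10 more than the 48 planned.

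**3. Work forward from 48.** Expected completers = 48 × 0.80 = 38.4. That meets 38 and is 7.6 short of 46.

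**4. Loss that each target allows from 48.** For 38: 1 − 38/48 = 20.8%. For 46: 1 − 46/48 = 4.2%.

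**5. Chance of reaching 46.** If each of 48 participants completes with probability 0.80, independently, then P(46 or more) = 0.8^46 × (1128 × 0.2² + 48 × 0.8 × 0.2 + 0.8²) = 0.8^46 × 53.44 = 0.0019, about 0.2%. The chance of 38 or more, on the same model, is about 64%.

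**6. Scale of the discrepancy (my assumptions, not the plan's).** With equal arms, a two-sided 5% test and 80% power, the noncentral-t detectable difference is about 0.85 SD at 23 per arm (46) and 0.93 SD at 19 per arm (38). The protocol states neither power, nor sidedness, nor allocation ratio, so these figures only indicate how much the choice of number matters.

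**7. What the 48 counts.** Suppose 48 means consents and a proportion s fail screening in addition to the 20% drop-out. Expected completers = 48 × (1 − s) × 0.80. This stays at or above 38 only if s ≤ 1 − 47.5/48 = 1.0%. The documents give no value of s, so the table uses assumed values.

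| Assumed screen failure s | Expected completers from 48 consents | Consents needed for 38 completers |
|---|---|---|
| 0% | 38.4 | 48 |
| 5% | 36.5 | 50 |
| 10% | 34.6 | 53 |
| 20% | 30.7 | 60 |
| 30% | 26.9 | 68 |

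**The case against.** The strongest defence is that the sample-size plan is coherent apart from one stray number. Thirty-eight is stated twice, including in the statistics section, and it yields the 48 exactly. The 46 could even be an inflated enrolment figure carried over by mistake, since 38 × 1.2 = 45.6, which rounds up to 46. That origin is plausible but is only an inference; nothing in the protocol confirms it. The defence supports 38 as the number to keep. It does not remove the contradiction, because Section 6.1.3 still states a binding requirement.

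A reader might also infer that 48 enrolled fails to deliver even 38 completers, because enrolment is counted at consent, before eligibility is checked. The documents do not support that. At the plan's own drop-out rate, 48 gives 38.4. A shortfall needs screen failures on top of the 20%, and the documents neither give a rate nor say whether the 20% already covers every loss after consent. Section 4.2.4 says the 48 is approximate, so it is not a hard cap. Sections 4.2.1 and 7.1 also use the word enrolled for people who are eligible: those with a known allergy to the drops are not enrolled, and those with dry eye disease are. On that usage, screen failures use up none of the 48. What stands is that this usage and Section 6.1.5 do not agree, and that the margin is only half a person (48 against 47.5).

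**Conclusion.** The contradiction is real and needs no outside assumption: 46 against 38 required completers. The figure of 46 is incompatible with 48 enrolled and 20% drop-out; it would take 58 enrolled, or a loss of no more than 4.2%. The 0.2% chance assumes independent drop-out at exactly 20%. A required sample size that differs between the population and statistics sections must be corrected.

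Thirty-eight is the only figure consistent with the rest of the document, but that is internal consistency and not scientific justification. A reader might take the 0.93 SD detectable difference as the reason for 38; it is calculated backwards from the number, under assumptions the plan does not state.

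The enrolment definition is a secondary ambiguity. It becomes a shortfall against 38 only if the 48 are consents, screen failures are additional to the 20%, and their rate exceeds about 1%.

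**What to change.** 1. In Section 6.1.3, change 46 to 38, so that it agrees with Sections 4.2.4 and 13.1.1 and with the 48 in the synopsis. The sponsor should first confirm that 38 is the intended number. If 46 was intended, Sections 4.2.4 and 13.1.1 must change to 46, and the enrolment in Section 4.2.4 and the synopsis to 58.
2. In Section 4.2.4 and the synopsis, state that 48 means randomised participants, that the 20% is loss after randomisation, and that screen failures do not count toward the 48. The consent-based definition in Section 6.1.5 can then remain, because the sample size no longer depends on it.
3. Do not add a power statement beside the 38 as though it had been the original rationale. If a detectable difference is reported, label it as calculated afterwards and give its assumptions.

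The cost is protocol wording. With 38 confirmed, a few more people may need to be screened to reach 48 randomised, but none beyond 48 are randomised. The stated requirement in Section 6.1.3 becomes the smaller of the two figures.

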### 6.1.4. Trial Duration

This study requires 2 visits of approx. 1-hour duration each. The study duration for each participant will be approximately 28 days.

### 6.1.5. Enrolment

A study participant is considered enrolled when they have signed the Participant Information Statement and Consent Form.

## 6.2. Primary Endpoint

The primary endpoint is a measurable difference in tear lipid layer thickness between Optimel Manuka eye drops and Systane Ultra eye drops after 4 weeks of daily use.

## 6.3. Secondary Endpoint(s)

The secondary endpoints are: a measurable difference in tear parameters such as tear breakup time and tear evaporation rate, and subjective symptoms after 4 weeks of daily use.

## SELECTION AND WITHDRAWAL OF PARTICIPANTS

### 7.1. Participant Selection

Participants with dry eye disease will be enrolled. Informed consent will be obtained prior to any clinical trial procedures being conducted. All participants will conform to the clinical trial entry criteria listed below:

#### 7.1.1. Inclusion Criteria

- Able to read and comprehend English and give informed consent as demonstrated by signing a record of informed consent;
- Adults aged 18 years and over with symptoms of dry eye;
- Ocular Surface Disease Index score of >12 at Screening;
- Not wearing contact lenses for 1 week prior to the study and for the duration of the study;
- Willing to use the study eye drops and refrain from using any other eye drops for the duration of the study;
- Willing to refrain from using the study eye drops within 4 hours prior to each study visit;
- Willing to comply with the study visit schedule and adhere to instructions as directed by the Investigator.

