#### 7.1.2. Exclusion Criteria

- Any active anterior segment disease excluding blepharitis;
- Use of any of the following medications (including steroids) up to 12 weeks prior to start of the study or during the course of the study:
  - Ocular medication, category S3 and above;
  - Any systemic or topical medications that will affect ocular physiology e.g. anti-acne medications such as Roaccutane and corticosteroid or immunosuppressant medications such as Hydrocortisone, Prednisolone and antihistamine medications such as Claritine.
- Use of any polyunsaturated fatty acid-containing dietary supplements (such as fish oil, evening primrose oil, linseed oil) for less than 12 weeks prior to the start of the study;
- Planned changes to intake of polyunsaturated fatty acid-containing dietary supplements and/or diet (including typical intake of fish) for the duration of the study;
- Use of any at-home eyelid warming treatments for less than 12 weeks prior to the start of the study, or planned changes to routine usage over the course of the study;
- Use of any of the following dry eye treatments up to 6 months prior to the start of the study or during the course of the study:
  - Intense Pulsed Light (IPL) therapy;
  - Blephasteam;
  - LipiFlow Thermal Pulsation treatment;
  - Punctal plugs.
- Any systemic disease that may affect ocular health e.g. Graves disease, and auto-immune diseases such as ankylosing spondylitis, multiple sclerosis and systemic lupus erythematosus;
- History of eye surgery within 6 months prior to enrolment in the study;

- Epilepsy or history of migraines exacerbated by flashing, strobe-like lights;
- Any known allergy to the ingredients in Systane Complete;
- Pregnancy or breastfeeding.

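### Baseline may be read at any interval after a participant's own eye drop, while day 28 is read at least 4 hours after a drop, and the two are subtracted

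*Combined protocol and SAP*

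**What the plan says.** Section 7.1 makes its entry list binding: "All participants will conform to the clinical trial entry criteria listed below". Two criteria in Section 7.1.1 deal with drops. On drops other than the study product, participants must be "Willing to use the study eye drops and refrain from using any other eye drops for the duration of the study". On timing, they must be "Willing to refrain from using the study eye drops within 4 hours prior to each study visit".

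The synopsis (Table 1) expects some entrants to be under treatment already: "Participant is willing to discontinue their use of any previous conventional dry eye treatment method commenced before the study throughout the study". Section 4.2.2 shows that the plan's term for such treatment covers lubricants: "the other group received a non-lipid based conventional ocular lubricant, Systane Ultra".

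Section 6 puts the whole of baseline into one visit: "Screening, randomization, informed consent, habitual visual acuity, OSDI, symptom survey, biomicroscopy, tear film assessment and dispensing eye drops". Under Section 6.1.5, enrolment begins at signed consent.

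Other exposures do have a look-back interval. For contact lenses the rule is "Not wearing contact lenses for 1 week prior to the study and for the duration of the study". Section 7.1.2 sets 12 weeks for "Ocular medication, category S3 and above" and for drugs affecting ocular physiology, and 6 months for IPL, Blephasteam, LipiFlow and punctal plugs.

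Section 13.1.3 uses the change from baseline to 28 days as the measure of treatment effect. It compares the arms by independent t-test or Mann-Whitney U test and mentions no adjustment for prior drop use.

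**The concern.** The 4-hour rule shows that its authors thought a recent drop could disturb the readings. In practice it protects only one of the two readings being subtracted. At day 28 it applies to everyone. At Visit 1 it does not reach a participant's own lubricant, and no other rule does.

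For a current user, the change score is then the effect of the study drop minus whatever the old drop was still doing at baseline. Nothing excludes prior users of either study product. Someone already on Systane Ultra at a similar dose and allocated to it would be expected to show a change near zero, however well the drop works. Baseline OSDI is taken at the same visit, so the symptom outcome is exposed as well.

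What is at stake is the precision of the change score and what each arm's change can be taken to mean.

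**Working it through.** **The plan's own figure.** Sections 4.2.4 and 13.1.1 ask for 38 completers, and Section 4.2.4 allows 20% dropout. 38 / (1 − 0.20) = 47.5, rounded up to 48, which matches the stated enrolment. (Section 6.1.3 says 46 must complete; 38 is used here.) The plan gives no power, effect size or SD, so the 38 itself cannot be derived.

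**The two readings side by side.**

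| | Visit 1 | Day 28 |
|---|---|---|
| Drops in use beforehand | Participant's own, if any | Study drop only |
| Rule on time since last drop | None for own lubricants | At least 4 hours |
| Role in Section 13.1.3 | Subtracted | Subtracted from |

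**Model.** Let p be the share of participants whose own lubricant still acts at baseline. Let w be that residual effect, in SDs of the change score. The residual is a property of the old drop, so it does not depend on allocation. With U = 1 for a current user and D for the study drop's effect:

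- Change = D(arm) − wU + error.
- Mean change in each arm = D(arm) − pw.
- Between-arm difference = [D(Optimel) − pw] − [D(Systane) − pw] = D(Optimel) − D(Systane). The residual cancels in expectation.
- Chance imbalance contributes a component with SD w × √(2p(1−p)/n) to the between-arm difference.
- The SD of change is inflated by s = √(1 + p(1−p)w²). This already contains the imbalance component, so the two are not added.
- Power ≈ Φ(0.93 / (s√(2/n)) − 1.96).

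**Inputs.** n = 19 per arm (38 completers; 1:1 is assumed, as the ratio is not stated). Alpha is 0.05 (Section 13.1.2), taken as two-sided. The documents give neither p nor w, so both ranges are assumptions. The difference of 0.93 SD is used only for scale: at 19 per arm it has 81.8% power by the normal approximation when no old drop is acting.

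| p | w (SD) | Per-arm shift pw (SD) | SD of imbalance component | s | Power |
|---|---|---|---|---|---|
| 0.2 | 0.25 | 0.05 | 0.032 | 1.005 | 81.4% |
| 0.2 | 0.50 | 0.10 | 0.065 | 1.020 | 80.3% |
| 0.2 | 1.00 | 0.20 | 0.130 | 1.077 | 75.8% |
| 0.5 | 0.25 | 0.125 | 0.041 | 1.008 | 81.2% |
| 0.5 | 0.50 | 0.25 | 0.081 | 1.031 | 79.4% |
| 0.5 | 1.00 | 0.50 | 0.162 | 1.118 | 72.7% |
| 0.8 | 0.25 | 0.20 | 0.032 | 1.005 | 81.4% |
| 0.8 | 0.50 | 0.40 | 0.065 | 1.020 | 80.3% |
| 0.8 | 1.00 | 0.80 | 0.130 | 1.077 | 75.8% |

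For comparison, the standard error of one arm's mean change is 1/√19 = 0.229 SD. The per-arm shift therefore runs from about 0.2 standard errors (0.05/0.229) to about 3.5 (0.80/0.229). If p or w is zero, there is no effect at all.

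**The case against.** The strongest reply is that the plan compares drops, not time points. The objective (5.1), primary endpoint (6.2), efficacy parameters (11.1) and tests (13.1.3) are all between arms. No paired or within-arm test is planned, and the hypothesis in 5.2 is most naturally read the same way. Both arms stop old drops under one rule, and starting from habitual care is a legitimate switch design. All of this stands, and it limits the harm to noise and interpretation.

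It also stands that a longer wash-out would not make the per-arm change a clean estimate. Participants are selected on OSDI above 12 and there is no untreated arm, so regression to the mean and time effects would remain. Nor do the documents show that a lubricant leaves any residual effect on lipid layer thickness.

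Three other replies carry less weight.

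- The 12-week bar on topical drugs affecting ocular physiology might be stretched to cover lubricants. Its examples are anti-acne, steroid, immunosuppressant and antihistamine drugs, and the synopsis carries that bar alongside the criterion that admits people on existing dry eye treatment.
- Read literally, the 4-hour rule would bind someone already using one of the two study products before Visit 1 as well. That is arguable, but it leaves every other lubricant uncovered.
- Medications are recorded at Visit 1, and the synopsis gives the investigator discretion to exclude. No rule says what to do with a recent drop.

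**Conclusion.** The gap is real and minor. Measurement conditions differ between the two visits for anyone using their own drops at entry, because the only timing rule omits those drops. Over the assumed ranges, the between-arm cost is between 0.4 and 9.1 percentage points of power (81.8% to 81.4% or 72.7%). The per-arm change is uninterpretable for current users to an extent that the documents do not allow anyone to estimate.

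A reader might infer two stronger conclusions, and neither is supported.

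- *The primary comparison is biased.* It is not, in expectation: the old drop's residual is independent of randomised allocation and cancels. Chance imbalance in prior use is possible with 19 per arm, but that is noise.
- *Each arm's change shrinks by a known percentage.* A common proportional shrinkage in both arms would require the two study drops to have the same effect. In addition, the share of users and the size of the residual are not given.

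The conclusion assumes additive residuals, equal allocation, and participants who keep to the 4-hour rule at day 28.

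**What to change.** Reword the timing criterion in Section 7.1.1 along these lines, and add it to the synopsis: *Willing to use no eye drops of any kind, neither the study drops nor the participant's own lubricants, in the 4 hours before each visit.* Send it to candidates with the contact-lens instruction, which must already reach them a week ahead. At Visit 1, record the product and time of the last drop under the existing history and medications item in Table 4.

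The cost is one more pre-visit instruction and an occasional rebooked Visit 1. Sample size and number of visits are unchanged. The rule makes the two readings comparable in time since the last drop. It does not remove longer-lasting effects of earlier drops, and it may do less for OSDI than for the tear film if the questionnaire looks back further than a few hours.

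A 1-week wash-out before Visit 1 would go further but is optional. It withdraws symptomatic treatment before consent, so it needs ethics committee agreement or a separate screening visit, and it may lose some of the more symptomatic candidates.
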